**Comparing blood loss and visualization after the preoperative use of topical 0.05%
Oxymetazoline versus 1:1000 epinephrine prior to endoscopic sinus surgery**

NCT03228914

Version Date: 08/02/2017

Protocol Title: Comparing blood loss and visualization after the preoperative use of topical 0.05% Oxymetazoline versus 1:1000 epinephrine prior to endoscopic sinus surgery.

Principal Investigator: [name]

Co-Investigators: [name]
[name], PhD
[name]

Study Coordinator: N/A

Population: Patients undergoing endoscopic sinus surgery (ESS) for CRS with or without nasal polyposis

Number of Sites: Single site

Study Duration: Study will continue until 50 patients are enrolled, likely 6 months to 1 year

Subject Duration: Study intervention will only be at the time of surgery. Normal surgery post-operative visits will occur with no additional study obligations

General Information

The study will be a single center prospective randomized double blinded study to compare blood loss and visualization of the surgical field following the preoperative use of pledgets soaked in 0.05% Oxymetazoline solution or 1:1000 concentrated Epinephrine.

Background Information

The development of functional endoscopic sinus surgery (FESS) in the early 1970s revolutionized the treatment of sinus disease by allowing for magnified direct visualization of complex sinus anatomy. FESS has now become by far the preferred surgical treatment modality of Otolaryngologist for the treatment of chronic sinus disease.⁸ The goals of FESS are to improve aeration and drainage of the paranasal sinuses by the meticulous removal of diseased air cells thereby reducing the frequency of infections.^{7,8} Due to the significant vascularity of the area bleeding presents one of the primary challenges in endoscopic sinus surgery as even slight hemorrhage can cause a dramatic reduction in visibility of the surgical field which can lead to prolonged operative time and increased risk of complications.^{2,3,5}

The use of several topical vasoconstrictors prior to endoscopic sinus surgery including cocaine, norepinephrine, epinephrine, phenylephrine and oxymetazoline have been described in the literature.^{3,5} Historically topical cocaine was used very commonly but has fallen out of favor given the addictive potential and associated side effects of tachycardia, hypertension and enhancement of the excitatory effects of epinephrine.^{3,5,6} The use of phenylephrine, a selective alpha agonist, has also been largely abandoned due to its unacceptable side effect profile including hypertensive crisis, cardiopulmonary compromise, pulmonary edema, and death.^{3,5}

Due to its favorable safety profile the use of Oxymetazoline has become increasingly popular.^{4,5,6} However, some authors believe the vasoconstrictive properties of oxymetazoline are inferior which could potentially lead to increased intraoperative hemorrhage. Desires for improved control of intraoperative hemorrhage and visualization has led to increased interest in the use of concentrated epinephrine prior to FESS.^{4,5,9,14}

Concentrated epinephrine has been demonstrated to be safe when applied topically.^{5,9} There have been reported adverse events and even deaths related to the mistaken submucosal injection of concentrated epinephrine.^{5,9,13,14} This risk can be successfully mitigated with careful preparation as well as dyeing of the more concentrated epinephrine solution with either surgical marking pens or fluorescein strips (FULGLO; Akorn Pharmaceuticals, Lake Forest, IL) to differentiate them from local anesthetic intended for injection.^{5,14} When used as intended epinephrine has been demonstrated to have an excellent safety profile.^{3,5,14} To date there have been no studies directly comparing the effects of oxymetazoline and epinephrine for preoperative vasoconstriction prior to FESS.^{3,11}

Objectives

Aim 1: Compare the Surgical field during functional endoscopic sinus surgery after the use of 0.05% Oxymetazoline or 1:1000 concentrated Epinephrine for decongestion

Hypothesis: There will be improved visualization in the concentrated epinephrine arm.

Aim 2: Compare the blood loss functional endoscopic sinus surgery after the preoperative use of 0.05% Oxymetazoline or Epinephrine

Hypothesis: There will be less bleeding in the epinephrine arm

Aim 3: Compare the surgical time to complete one sinus side during functional endoscopic sinus surgery after the preoperative use of 0.05% Oxymetazoline or Epinephrine

Hypothesis: There will be no difference in surgical time

Study Design

The study will be a single center prospective randomized double blinded pilot study to compare blood loss and visualization of the surgical field following the preoperative use of pledgets soaked in Oxymetazoline or Epinephrine.

The inclusion criteria will be patients undergoing bilateral endoscopic sinus surgery (ESS) in which the same sinuses and procedures on both sides are the same for CRS with or without nasal polyposis. Exclusion criteria will be pregnancy, known coagulopathy, an international normalized ratio greater than 1.3, a partial thromboplastin time greater than 50 seconds, use of non-steroidal anti-inflammatory drugs in the last 10 days (2 or more doses), use of any antiplatelet agents (eg, warfarin, clopidogrel, berlinta) poorly controlled hypertension with a

preoperative systolic blood pressure of 160mm Hg or greater or a diastolic blood pressure of 90mm Hg or greater, or having any adverse reaction to topical epinephrine or oxymetazoline.

The study will be a paired design study with one nasal cavity receiving epinephrine and the other receiving oxymetazoline. The 1:1000 epinephrine and oxymetazoline solutions both comes in a 30cc vial and each pledget will be wrung out in a similar fashion to keep volume administered similar. The side each drug will be placed on will be randomized using a block randomization scheme on the day of surgery with a block size of four. Two pledgets with the associated medication will be placed into the nasal cavity; one along the floor of the nose and another directed towards the middle meatus.

As a part of routine preoperative workup all patients receive preoperative computed tomography scans of the paranasal sinuses with a navigation protocol. These scans will be assessed using the Lund-Mackay staging system, a standardized radiological grading system used to evaluate CT scans of chronic rhinosinusitis patients. The sinonasal mucosa will also be scored by the surgeon on the day of surgery using a mucosal grading system we have used previously which was modified from a mucosal grading system originally used for grading patients with allergic fungal rhinosinusitis.²

The patients will be recruited from the practices of 3 fellowship trained rhinologists within our institution.

All data will be deidentified and assigned a random number. Data will be stored on a password protected file on a password protected computer.

Our primary endpoint will be to compare surgical field visualization after the use of epinephrine or Oxymetazoline using the Boezaart grading scale, an inexpensive standardized rating scale used to analyze surgical field visualization during sinus surgery. The operative field will be rated at the conclusion of the procedure by the surgeon. A representative 1 minute video will also be selected for each side. These videos will be blindly reviewed and rated by all 3 surgeons using the Boezaart scale.

Our secondary endpoint will be to compare the amount of blood loss use after the use of epinephrine or Oxymetazoline. This will be done by subtracting the amount of irrigation used from the volume collected in the suction canisters to estimate blood loss. The Neptune 2 Waste Management System (NWMS, Stryker, Kalamazoo, Michigan), a closed suction system that digitally measures the amount of fluid suctioned will be used for more accurate measuring of fluid suctioned.

Both Oxymetazoline and Epinephrine soaked pledgets are routinely used preoperatively before sinus surgery both within our institution and nationally. The choice of which is based on surgeon preference. Both have well established safety profiles. (Higgins, Korkmaz, Orlandi)

Study Population

The inclusion criteria will be patients undergoing endoscopic sinus surgery (ESS) for CRS with or without nasal polyposis. Exclusion criteria will be pregnancy, known coagulopathy, an international normalized ratio greater than 1.3, a partial thromboplastin time greater than 50 seconds, use of non-steroidal anti-inflammatory drugs in the last 10 days (2 or more doses), poorly controlled hypertension with a preoperative systolic blood pressure of 160mm Hg or greater or a diastolic blood pressure of 90mm Hg or greater, or having any adverse reaction to topical epinephrine or oxymetazoline.

The patients will be recruited from the practices of 3 fellowship trained rhinologists within our institution.

Study Procedures

As a part of routine preoperative workup all patients receive preoperative computed tomography scans of the paranasal sinuses with a navigation protocol. These scans will be assessed using the Lund-Mackay staging system, a standardized radiological grading system used to evaluate CT scans of chronic rhinosinusitis patients. The sinonasal mucosa will also be scored by the surgeon on the day of surgery using a mucosal grading system.

All patients will undergo general anesthesia using a standardized anesthesia protocol using Propofol and inhalational anesthetics. Total intravenous anesthesia will not be used. Preoperative Decadron will not be used in patients enrolled in the study.

The patients will have pledgets soaked in epinephrine 1:1,000 in one nasal cavity and pledgets soaked in oxymetazoline 0.05% to the contralateral side for topical vasoconstriction and decongestion. Both 1:1000 epinephrine and oxymetazoline solutions comes in a 30cc vial and each pledget will be wrung out in a similar fashion to keep volume administered similar. The solutions will be prepared prior to the procedure so that the surgeon will be blinded to which topical vasoconstrictor is used on each side. All topical solutions will be dyed with fluorescein strips (FULGLO; Akorn Pharmaceuticals, Lake Forest, IL) to differentiate them from local anesthetic intended for injection. Laterality of the study medication will be randomized through block randomization with a block size of four.

Following topical vasoconstriction, pledgets will be removed and all patients will receive injections of 1% lidocaine with epinephrine 1:100,000 into the middle turbinate and sphenopalatine area as is routinely performed prior to sinus surgery. Complete functional endoscopic sinus surgery will then be performed as indicated using typical sinus surgery instruments. Intraoperative imaging will be recorded and deidentified for later review by blinded reviewers.

The operative field will be rated at the conclusion of the procedure by the surgeon. A representative 1 minute video from each side will later be blindly reviewed and rated by all 3 surgeons using the Boezaart scale.

There will be no additional visits or time commitments for the patients outside of routine post-operative follow up.

Data and Safety Monitoring

All data will be deidentified and assigned a random number. Moreover, the deidentified data will be stored on a password protected file on a password protected computer.

No adverse events are anticipated. The study should provide no additional risk to the patient.

Any potential adverse events or unanticipated problems will be monitored by the research team and reported as discovered. The research team has a pre-scheduled monthly meetings where this study will be discussed.

Statistics

Statistical significance will be defined as less than 0.05. For quantitative data a 2-tailed paired t-test will be used. Categorical data will be compared using the McNemar's test. For non normally distributed data a Wilcoxon rank-sum test will be used. All patients who are administered both randomized preoperative topical vasoconstrictors will be included in the study.

The blood loss of 355 ± 393 mL seen in sevoflurane group from a previous study we performed in which we used oxymetazoline was used to calculate sample size.² With a proposed difference of 150ml of blood loss with a targeted power of 0.8 and a targeted Type 1 error rate of 5% a sample size of 50 was calculated we will plan to enroll 50 patients.

Ethics

No other IRB approval will be sought.

Informed consent will be obtained by one of the study investigators at the patient's preoperative visit in clinic or in the preoperative waiting area.

All data will be deidentified and assigned a random number. Data will be stored on a password protected file on a password protected computer.

Data handling and record keeping

All data will be deidentified and assigned a random number. Data will be stored on a password protected file on a password protected computer in the principal investigators office. All videos obtained will be de-identified and kept at the principal investigator's password protected computer in a locked office.

Quality control and assurance

Quality of video data and photographs will be assessed intraoperatively. A Storz representative will be available to aid with video equipment if technical difficulties were to occur.

There are no plans to have third party monitoring.

Publication Plan

We plan to submit the paper for publication to a high-quality ENT or Rhinology journal. Results will be available to the patients if requested.

References

1. Anderhuber, W., C. Walch, E. Nemeth, H. J. Semmelrock, A. Berghold, G. Ranftl, and H. Stammberger. "Plasma Adrenaline Concentrations during Functional Endoscopic Sinus Surgery." *The Laryngoscope* 109, no. 2 Pt 1 (February 1999): 204–7.

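### Aim 3 predicts no difference in surgical time, but the plan has only difference tests, which can contradict that prediction and cannot establish it

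*Combined protocol and SAP*

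**What the plan says.** The Objectives list three aims. Aims 1 and 2 predict an advantage for epinephrine; for blood loss the wording is "Hypothesis: There will be less bleeding in the epinephrine arm". Aim 3 is to "Compare the surgical time to complete one sinus side during functional endoscopic sinus surgery" under the two drugs, and its prediction runs the other way: "Hypothesis: There will be no difference in surgical time".

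The Statistics section makes no distinction between the aims. It says "Statistical significance will be defined as less than 0.05". For continuous outcomes, "For quantitative data a 2-tailed paired t-test will be used", and "For non normally distributed data a Wilcoxon rank-sum test will be used". McNemar's test is assigned to categorical data. Nowhere do the documents mention a confidence interval, an equivalence margin or how a non-significant result will be read.

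The sample size rests on blood loss: "With a proposed difference of 150ml of blood loss with a targeted power of 0.8". The Study Design section names field visualization as the primary endpoint and blood loss as the secondary one. It does not name time as an endpoint, and it describes the study as a pilot.

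**The concern.** A test for a difference suits Aims 1 and 2, because a significant result in the predicted direction is evidence for them. In Aim 3 the predicted state is the null hypothesis of the planned test. The test can therefore count against the prediction but never for it. The only outcome consistent with the prediction is a failure to reject, and that can also arise when a real difference exists and the data are too few or too variable to show it.

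The protocol's own reasoning makes a time difference plausible. Background Information says that even slight bleeding "can cause a dramatic reduction in visibility of the surgical field which can lead to prolonged operative time", and Aims 1 and 2 expect a better field and less bleeding with epinephrine. If Aim 3 were reported only as p>0.05, readers would not know whether the data had excluded a sizeable time difference or had simply not resolved one.

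**Working it through.** **Plan's own figure.** There is none to reproduce for time: no expected time, SD, margin or power is given. The stated sample size of 50 belongs to blood loss and is used here only as the number of pairs.

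**Inputs**
- n = 50 pairs, from the planned enrolment (Statistics) and one nasal cavity per drug (Study Design). This assumes that every patient contributes a time for both sides.
- Two-sided 0.05 and the paired t-test (Statistics).
- True differences d of 0.2 to 0.5, in units of the SD of the within-patient time difference. These are illustrative assumptions.

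**Step 1: what each result says about the hypothesis**

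| Result | Aims 1 and 2 (difference predicted) | Aim 3 (no difference predicted) |
|---|---|---|
| p<0.05 | supports, if in the predicted direction | contradicts |
| p>0.05 | does not support | consistent with it, does not establish it |

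**Step 2: how often p>0.05 occurs when there is a real difference.** The t statistic follows a noncentral t distribution with 49 degrees of freedom and noncentrality d × √50. The critical value is t(0.975, 49) = 2.010.

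| True difference (SD of paired difference) | Noncentrality | Power | Chance of p>0.05 |
|---|---|---|---|
| 0.2 | 1.414 | 0.284 | 72% |
| 0.3 | 2.121 | 0.548 | 45% |
| 0.4 | 2.828 | 0.792 | 21% |
| 0.5 | 3.536 | 0.934 | 7% |

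**Step 3: what the bare statement p>0.05 leaves open.** The 95% CI half-width is h = 2.010 / √50 = 0.284 observed SD. For the paired t-test, p>0.05 means that the absolute mean difference is below h. The limit furthest from zero is the absolute mean difference plus h, so it lies between h = 0.284 and 2h = 0.568 observed SD. The bare statement does not say where in that range it falls; the interval does.

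**Step 4: what a positive claim would require.** The 90% CI half-width is t(0.95, 49) / √50 = 1.677 / 7.071 = 0.237 SD. By simulation with a true difference of zero and 50 pairs, the 90% CI lies wholly inside a margin of 0.3, 0.4 or 0.5 SD in 35%, 75% and 93% of trials. Whether 50 pairs could support a claim of no important difference therefore depends on a margin and an SD that the documents do not give.

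**Step 5: the non-normal branch.** The rank-sum test named there ignores the pairing, which is an issue in its own right. It matters for the fix, because a paired interval would then sit beside an unpaired p-value. In a simulation of 50 pairs with Laplace errors and a true difference of 0.3 SD, the signed-rank and rank-sum tests disagreed on significance in about 18%, 34% and 53% of trials at assumed within-patient correlations of 0.3, 0.5 and 0.7. The exact percentages depend on the assumed error model; the direction is what matters.

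**The case against.** The strongest reply is that Aim 3 sets out to compare, that a two-sided paired t-test is a legitimate comparison, and that the hypothesis may be no more than an expectation. This largely stands. A reader might infer that the investigators intend to declare the drugs equivalent on time when p>0.05. The documents do not say so, and no decision in them turns on such a claim. What remains is that they offer no other way to judge the stated hypothesis.

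Second, no interval is planned for any aim, and one can be computed later without new data. Both are true. The omission bears more on Aim 3 because there the hypothesis test cannot deliver the predicted conclusion.

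Third, an exact p-value is more informative than this point might suggest. With n = 50 it fixes the absolute t statistic, and so the interval in SD units apart from its sign. That is correct. The loss described above applies to the bare statement p>0.05, and even that caps the furthest limit at 0.57 observed SD.

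Fourth, 0.28 to 0.57 SD cannot be called important or trivial without an SD for time. This also stands. A reader might infer that the trial is too small for Aim 3, but the documents do not allow that conclusion in either direction.

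Finally, the documents do not define when timing of a side starts and stops. That is a separate gap, which the change below does not close.

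**Conclusion.** The point holds, and it is minor. The analysis planned for Aim 3 can contradict its hypothesis but cannot establish it, and no interval, margin or reading rule fills the gap. With 50 complete pairs, a non-significant result is more likely than not at a true difference of 0.2 SD (72%) and close to even at 0.3 SD (45%).

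These figures assume approximately normal paired differences and the paired t-test. They are in SD units because nothing in the documents converts them to minutes. The weight is limited because time is neither the primary nor the named secondary endpoint, the sample size was set on blood loss, and the study is a self-described pilot. The point does not show that an equivalence design is required: Aim 3 can be kept as a comparison with a stated expectation, provided that the result is reported as an estimate with its uncertainty.

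**What to change.** Add to Statistics:

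> For surgical time per side the main result will be the mean paired difference (epinephrine minus oxymetazoline) with its 95% CI. If the paired differences are clearly non-normal, the Hodges-Lehmann estimate (pseudo-median of the paired differences) with its 95% CI will be reported, together with the paired Wilcoxon signed-rank test in place of the rank-sum test. A result of p>0.05 will not be reported as evidence of no difference.

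The Aim 3 hypothesis may stay as an expectation. Only if the investigators want to claim no important difference do they need a margin in minutes, fixed with its reason before data review, and the requirement that the 90% CI lie inside it.

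The cost is a few lines of text, with no extra patients, visits or measurements. The downside is that Aim 3 may end as inconclusive, which is the accurate report if the interval is wide.

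### Blood loss is not tied to a side, and nothing is read or cleared at the change of side, so the per-side values needed for the paired comparison are not secured

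*Combined protocol and SAP*

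**What the plan says.** On the design, Study Design states: "The study will be a paired design study with one nasal cavity receiving epinephrine and the other receiving oxymetazoline". On allocation it states: "The side each drug will be placed on will be randomized using a block randomization scheme on the day of surgery with a block size" (the size is given as four). The order in which the two sides are operated on is not mentioned anywhere.

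The secondary endpoint is introduced with: "Our secondary endpoint will be to compare the amount of blood loss use after the use of epinephrine or Oxymetazoline". The measurement rule follows: "This will be done by subtracting the amount of irrigation used from the volume collected in the suction canisters to estimate blood loss". The device is described as "a closed suction system that digitally measures the amount of fluid suctioned will be used for more accurate measuring of fluid suctioned".

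The plan names the side for other outcomes. For the video: "A representative 1 minute video will also be selected for each side". For time, Aim 3 is worded: "Compare the surgical time to complete one sinus side during functional endoscopic sinus surgery". Blood loss has no matching words.

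Study Procedures goes from pledget removal and local injection straight to surgery: "Complete functional endoscopic sinus surgery will then be performed as indicated using typical sinus surgery instruments". It has no step for reading the suction system, logging irrigation or clearing fluid between sides. Surgical time appears neither among the endpoints in Study Design nor in Study Procedures.

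Statistics plans a two-tailed paired t-test for quantitative data. It sizes the study on blood loss: 355 ± 393 mL from an earlier study that used oxymetazoline, a difference of 150 mL, power 0.8 and a 5% type 1 error, giving 50 patients.

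**The concern.** A paired t-test on blood loss needs two numbers from each patient, one per nasal cavity. Each number is itself a difference between suctioned volume and irrigation. Both volumes therefore have to be split at the same moment. The protocol does not say when either is read. If the reading at the change of side is missed, no later analysis can divide the volume between the drugs.

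A reading alone is not enough. Blood still lying in the first cavity or nasopharynx when the reading is taken, or oozing from it afterwards, is suctioned during work on the second side and credited to the other drug. That mixes the two arms within the patient and shrinks the contrast.

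Aim 2 and the sample size both rest on this endpoint.

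**Working it through.** **1. The plan's own figure.** Inputs from Statistics: difference 150 mL, SD 393 mL, power 0.8, two-sided 5%. If 393 mL is taken as the SD of the within-patient differences (an assumption), n = (393 × 2.8016 / 150)² = 53.9, so 54 patients; the t-based figure is 56. One-sided versions give 43 and 44. Two independent groups would need 108 per arm. The stated 50 is not reproduced exactly; it would need an SD of differences of about 379 mL, which is not given. The present point does not depend on this. At n = 50 and SD 393 mL, the paired t-test has power 0.754, which is the baseline below.

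**2. Carry-over model.** Let E and O be the true losses on the epinephrine and oxymetazoline sides. Let f be the share of first-side loss collected during the second side. The documents do not give f.

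- Epinephrine side first: measured O − E = (O + fE) − (1 − f)E = (O − E) + 2fE.
- Oxymetazoline side first: measured O − E = (1 − f)O − (E + fO) = (O − E) − 2fO.
- Average over balanced order: (O − E) + fE − fO = (1 − f)(O − E).

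The shrinkage factor (1 − f) does not depend on the size of E or O.

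**3. Numbers.** Take O − E = 150 mL. For the order-specific columns, assume O = 355 and E = 205 mL per side. Power is for n = 50 with the underlying SD of differences held at 393 mL.

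| f | Epinephrine first (mL) | Oxymetazoline first (mL) | Balanced mean (mL) | Power, shrinkage only | Power, with order variance |
|---|---|---|---|---|---|
| 0 | 150 | 150 | 150 | 0.754 | 0.754 |
| 0.1 | 191 | 79 | 135 | 0.663 | 0.654 |
| 0.2 | 232 | 8 | 120 | 0.562 | 0.530 |
| 0.3 | 273 | −63 | 105 | 0.457 | 0.399 |

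Example for f = 0.1: 150 + 2 × 0.1 × 205 = 191; 150 − 2 × 0.1 × 355 = 79; mean 135.

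**4. The order effect.** Each patient's difference moves by ±f(E + O) around the balanced mean. At f = 0.1 this is 0.1 × 560 = 56 mL, so the SD of differences rises from 393 to √(393² + 56²) = 397 mL. Over 50 patients whose order is unrelated to drug, this contributes 56/√50 = 7.9 mL to the standard error. This is noise and chance imbalance. An analysis that includes order can remove it, which is why the shrinkage-only column is the relevant one after adjustment.

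**5. Sensitivity to the 355 mL.** The documents do not say whether 355 mL is per side or per patient. If it covers both sides, O = 177.5 and E = 27.5 mL, and f(E + O) is 20.5, 41 or 61.5 mL at f = 0.1, 0.2 or 0.3. The balanced means of 135, 120 and 105 mL do not change.

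**The case against.** The best defence is that per-side measurement is plainly intended. The endpoint sentence compares the two drugs, the design is paired by nasal cavity, the test is paired, the canisters are in the plural, and a digital system can be read at any moment. All of that stands. A reader might infer that the plan takes a single volume for the whole operation and so yields no drug comparison at all. The documents do not support that: no sentence says so, and the design and the test point the other way. Intent, however, does not give the three surgeons' practices a common procedure, and the reading exists only if it is taken at the time.

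A reader might also infer that operating on one side first biases the drug comparison. That goes too far. Drug laterality is randomized, and Study Procedures has the solutions prepared so that the surgeon does not know which is on which side. If blinding holds, order cannot follow drug, so a first-versus-second-side effect mainly adds variance and chance imbalance. Only the shrinkage remains as expected bias, and it runs toward no difference.

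Nor does Aim 3 rest on a whole-operation time, since it names one side as its unit. What is missing is time in the endpoint list and in the procedures.

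Finally, f is assumed and blood loss is the secondary endpoint. Both are fair limits on the weight of the point. Neither removes the gap in the definition.

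**Conclusion.** The concern holds as a gap in how an intended per-side measurement is specified. It is a worthwhile, inexpensive improvement, and it should be settled before the first case because missed readings cannot be reconstructed.

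The gap itself follows from the text and needs no assumption. The size of the carry-over effect does need one: for assumed f of 0.1 to 0.3 and balanced order, a true 150 mL difference would be estimated as 135 to 105 mL. Power would fall from 0.754 to between 0.663 and 0.457 from shrinkage alone, further assuming an SD of differences of 393 mL. The consequence is an understated effect and lost power, not an expected false difference between the drugs.

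**What to change.** In Study Design and Study Procedures:

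- Define blood loss for a side as the increase in the Neptune volume during that side minus the irrigation used during that side.
- At the change of side, once residual fluid from the first side has been suctioned, record the Neptune reading, cumulative irrigation and clock time. Repeat all three at the end of the second side.
- Record which side was operated on first and any return to the first side, with the volumes collected then.
- In Statistics, include side order in the analysis of the within-patient differences. Clearance does not stop later oozing. Adjusting for order removes the order effect but not the shrinkage, so clearance and adjustment are both needed.
- Use the same clock times for Aim 3, and list surgical time per side as an endpoint.

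These are measurement steps and do not prescribe which side is operated on first. The cost is a brief pause at the change of side, a few protocol sentences and a few data-sheet lines, on equipment already in use and with no extra patients. Because the front matter lists no study coordinator, the protocol should also name the role that writes down the readings.

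### Side is the only randomised factor and is balanced in blocks of four, but the planned paired tests leave it out; if the two sides differ on average, some power is lost, and adding a side term costs almost nothing

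*Combined protocol and SAP*

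**What the plan says.** Study Design describes a split-nose comparison: "The study will be a paired design study with one nasal cavity receiving epinephrine and the other receiving oxymetazoline". The only thing left to chance is which side gets which drug: "The side each drug will be placed on will be randomized using a block randomization scheme on the day of surgery". Study Procedures repeats this and gives the block size: "Laterality of the study medication will be randomized through block randomization with a block size of four".

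Statistics names three tests. Its rule for measured outcomes reads: "For quantitative data a 2-tailed paired t-test will be used". Outcomes that fall into categories go to McNemar's test. Where normality fails, the plan turns to a third test: "For non normally distributed data a Wilcoxon rank-sum test will be used". The significance level is 0.05. No side term, stratified test or adjusted analysis appears anywhere in the document.

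Study Design limits entry to patients who have the same sinuses and procedures done on both sides. No figure is given for any left-right difference in visualisation, blood loss or time.

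**The concern.** Blocking on a factor forces that factor to balance. The usual rule is then to carry it into the analysis, because otherwise the analysis counts as noise a source of variation that the design has already removed from the estimate.

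Here each full block of four puts epinephrine on the left in two patients and on the right in two. Suppose that one side is on average harder to work on, for example because of access or the surgeon's position. That difference enters each patient's epinephrine-minus-oxymetazoline value as +L or -L. It cancels from the mean but stays in the standard deviation that the paired t-test uses.

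What is at stake is precision: confidence intervals wider than they need be, a true type 1 error below the nominal 5%, and some lost power. It would apply to each aim whose outcome has such a difference.

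**Working it through.** **Inputs from the documents.** 50 patients; blocks of four (Study Design, Study Procedures); two-tailed paired t-test and McNemar's test at 0.05, target difference 150 mL, SD 393 mL from an earlier study, power 0.80 (all Statistics). **Assumed:** L, because the documents give none, and the SD of the within-patient difference, because 393 mL describes the spread of blood loss between patients.

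**The plan's own figure.** If 393 mL is taken as the SD of the difference, the paired formula gives ((1.960 + 0.842) × 393 / 150)² = 53.9, so 54 patients (56 with the t distribution). The stated 50 is not reproduced. With 50 patients the paired t-test has power 0.754. This is a separate matter and does not affect what follows.

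**Balance.** 50 = 12 × 4 + 2, so one blocked list splits 25/25 or at worst 26/24.

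**Model.** Let D be the epinephrine-side value minus the oxymetazoline-side value, with s = +1 if epinephrine is on the left and -1 if on the right: D = δ + sL + e, with SD(e) = σ.

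- Mean of D: L is multiplied by the mean of s, which is 0 at 25/25 and 2/50 = 0.04 at 26/24, so L nearly vanishes. The true variance of the mean is close to σ²/50.
- Sample variance of D: about σ² + L². The estimated standard error is therefore too large by √(1 + (L/σ)²).
- Effective number of patients: 50 / (1 + (L/σ)²).

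**Simulation.** Trials of 50 patients in permuted blocks of four with normal errors. The drug effect is 0.404σ, which gives 80% power for 50 pairs at L = 0.

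| L/σ | Variance factor | Effective n | Type 1 error, plain | Power, plain | Power, side included |
|---|---|---|---|---|---|
| 0 | 1 | 50 | 5% | 80% | 80% |
| 0.1 | 1.01 | 49.5 | 5% | 80% | 80% |
| 0.25 | 1.0625 | 47 | 4.3% | 78% | 80% |
| 0.5 | 1.25 | 40 | 3% | 72% | 80% |

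Separate runs differ by a few tenths of a point. With side included, type 1 error stays at about 5% in every row.

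**In millilitres.** With σ = 393 mL (assumed), the last three rows correspond to L of 0.1 × 393 = 39 mL, 0.25 × 393 = 98 mL and 0.5 × 393 = 197 mL. For the 150 mL target, power with the plain test is 0.750 at L = 50 mL, 0.733 at 100 mL and 0.669 at 200 mL, against about 0.753 with side included. If σ were 200 mL (assumed), L = 100 mL would already give a type 1 error of 0.029.

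**Source of the conservatism.** Under simple, unblocked randomisation the plain test's type 1 error stays at about 5% for every L. The shortfall comes from blocking that the analysis ignores.

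**McNemar's test.** With 60% of pairs discordant (assumed), and one side worse in 60%, 70% or 80% of discordant pairs, the asymptotic type 1 error is 0.049, 0.041 or 0.029.

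**What a side term does not reach.** Asymmetry that varies at random between patients (SD 200 mL, assumed) leaves the plain test's type 1 error at 0.050. It is genuine error. Surgeon-specific side effects of +0.5, -0.5 and 0 SD leave both analyses at about 73.8% power.

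**The case against.** The case against treating this as a defect is substantial, and most of it stands.

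- **The loss is conditional.** It arises only if a common mean left-right difference exists. Nothing in the documents reports one, and the requirement for the same procedures on both sides limits it. At 0.1 SD the loss is negligible. With σ = 393 mL, the 0.5 SD row needs a side effect of 197 mL, larger than the 150 mL drug effect the trial is sized for. This stands.
- **The planned paired tests are valid.** A reader might infer that they are biased or give false positives. They do neither: the estimate is unbiased and type 1 error is at or below about 5%. A plain paired test is defensible in what Study Design calls a pilot. This stands.
- **Not every asymmetry is involved.** A reader might infer that all left-right variation is wrongly counted as error, or that a side term always restores 80% power. Both are too strong. Patients come from the practices of three surgeons, no stratification by surgeon is stated, and handedness or position effects could differ in direction between them.
- **The t-test may not be the test used.** The primary outcome is a Boezaart grade, and blood loss at 355 ± 393 mL is probably skewed. This stands in part. McNemar's test shows the same effect, so the point is not confined to the t-test. The figures do not describe the rank-sum test as written: it is an unpaired test in a paired design, which is a separate problem.

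What remains is that side is known for every patient, and including it costs almost nothing when L is zero (80.1% power without it, 80.0% with it).

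**Conclusion.** The plan balances side by design and then omits it from the paired t-test and McNemar's test. If a common mean left-right difference exists, those tests are conservative. Power of 80% stays at about 80% for L up to 0.1 SD, and falls to about 78% at 0.25 SD and 72% at 0.5 SD.

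These sizes rest on assumed values of L, on normal differences and on one L shared by all patients and surgeons. The documents do not support saying that power is in fact lost on all three aims, because they give no left-right figure for any of them. The mechanism is certain and its size in this trial is unknown. It is a low-cost improvement in efficiency.

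**What to change.** In Statistics, prespecify before unblinding:

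- **Quantitative outcomes.** Regress the epinephrine-minus-oxymetazoline difference on laterality (+1 for epinephrine on the left, -1 for the right). Report the average of the two laterality-group means as the drug effect, with its 95% confidence interval, on 48 degrees of freedom for 50 patients.
- **Ordinal or non-normal outcomes.** Apply the rank-sum test to the left-minus-right differences, comparing the epinephrine-left group with the epinephrine-right group. In this form the rank-sum test respects the pairing.
- **Binary outcomes.** Among discordant pairs, tabulate which side is worse against laterality group and test that two-by-two table, in place of McNemar's test.

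The cost is a short addition to Statistics and one degree of freedom. No new data, patients or procedures are needed.
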